4.7. Schedule of Events

The schedule of events can be seen in Table 1. Patients will be seen and consented at a screening visit to determine eligibility. It is anticipated that most if not all of the serologic data needed to qualify the patient will be available by review of electronic records at the screening visit. If not, one or more of the serologic HBV markers will be tested at screening. The serologic studies for HBV must have been done within the past year. Turnaround times are less than 5 days and so there should be no lagging data needed at the time the patients receive their first dose of vaccine 28-30 days later. There will also be a 28-30 day window between the first vaccine inoculation visit and the second vaccine inoculation visit. The 12, 24, and week 60 visits will have a one week \pm window.

In the event of an intercurrent acute illness that either places the patient at added risk or makes vaccine adverse event relatedness difficult to interpret, every effort will be made to bring the patient back when the illness is resolved and preferably no longer than one week of the initially specified time.

Heplisav-B vaccine will be delivered at the baseline/enrollment visit (visit # 2 considered to be day 0) and again 4 weeks later. In the unlikely event that anti-HBs titer is ≥ 300 mIU/mI after a single dose of vaccine, patients will not be given a second dose. All individuals who do not have protective levels of anti-HBs (> 10 mIU/mI) after two doses at week 8 will be given a third identical dose of vaccine at the week 12 visit.

Adverse events (e.g, localized skin reactions, fever) that occur soon after vaccination will be assessed by weekly telephone assessments and patients will be asked to record changes in underlying disease activity on a Patient Related Outcome Measurement form. These will be distributed at the enrollment visit and subsequent visits. They will initially be completed by the patient and completed as needed by the investigator and coordinators at all study visits. Data on all AEs will be recorded on an Adverse Event Data Capture form (Appendix 1). These will be filled out by the study coordinator in conjunction with the investigator at each visit.

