5.0. TRIAL OBJECTIVES

There are two co- primary objectives: (1.) To assess immunogenicity of Heplisav-B and (2.) to assess safety in medically immunosuppressed patients. The former will require assessing the proportion of patients who respond with seroprotective levels (>10 mIU/mI) of anti-HBs and who maintain this response until study completion at week 60. The second objective will require follow up of all patients for one year after the last dose of vaccine during which time all adverse events will be collected.

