10.1 Safety Endpoints

Patient safety is a co-primary objective of the study and the following endpoints will be considered and used for future reporting:

- 1. Proportion of subjects with unsolicited AEs after inoculation. All adverse events including those that are unsolicited will be recorded for a period of 28 days after vaccine administration, and at each visit changes in the patient's state of health will be recorded on the Appendix 1 (AE capture form) and as needed on the Appendix 2 form. To facilitate accurate reporting in real time, patients will be questioned at a weekly telephone assessment and seen by the principal investigator should this appear warranted. Photographic evidence by the patient may be requested between visits for certain AEs.
- 2. Proportion of subjects with SAEs. The study will capture all SAEs (and Grade 3 AEs) that occur through one year after the last dose of vaccine. To facilitate accurate reporting, all patients with these events will be seen within 48 to 72 hours and acted upon if needed. Follow up will continue until at least 52 weeks after the last dose of vaccination Data will be collected on the Appendix 1 safety form and in the case of Group A, Appendix 2 as well.
- 3. Proportion of subjects with MAAEs. All MAAEs that occur within one year of the last vaccine dose will be captured. Patients will be handled as in 2 Above.
- 4. Proportion of subjects with pIMMCs. This will be captured for a period of 52 weeks after the last dose of vaccine. Patients will be handled as in 2 and 3 above. Data will be reported on both the Appendix 1 and Appendix 2 safety forms.
- 5. Proportion needing an increase in immune suppressive medication. All concomitant medications used during the 28 day period following vaccination and those used to treat MMAEs or SAEs during a 12 month period after the last dose of vaccine will be recorded. Special attention will be given to new or dose adjusted immune suppressive medications that are needed to treat adverse events. Data will be captured in Appendix 1 (adverse event capture form) under the header "Type Intervention."

10.2 Further Safety Considerations:

- a. C-reactive protein blood testing will be used to assess augmentation of inflammatory disease activity in Group A.

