10.5 Adverse Event Reporting

All grade 3 or 4 adverse events will be reported simultaneously to the IRB and sponsor within one week and 72 hours, respectively. Should a death occur, notification of the IRB will be within 24 -48 hours of receipt of this information. Events will be conveyed to the IRB and if needed to the sponsor in both electronic and hard copy form along with whether or not the event was considered to be related to administration of the study drug. All relevant lab studies will be included in the correspondence. All Grade 1 and 2 AEs (for example, such as those related to reactogenicity of the vaccine) will be collected at each visit and reported to the sponsor in a yearly report.

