11.0. STATISTICAL PLAN

11.1. Statistical Methods

The study is exploratory and as such descriptive statistics will be used. Continuous variables will be expressed as median values, range of values, and mean \pm standard deviation while categorical variables will be expressed as number (percentage). Qualitative and quantitative differences between subgroups will be analyzed by Chi-square or Fisher's Exact tests for categorical parameters and Student's t test or Mann Whitney test for continuous parameters as appropriate. Statistical significance will be taken as p < 0.05.

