^{** 5%} of recipients of anti-HBc donor liver are anticipated to be anti-HBc positive. These patients will be excluded if anti-HBs also > 20 mIU/ml. Patients transplanted for HBV infection are anticipated to be anti-HBc positive

[#] If anti-HBs level remains < 10 mIU/ml

TABLE 1. Study Participation Table

	Visit 1: Screening	Visit 2 Enrollment/ Baseline	Visit 3 4 Week Follow up (+/- 3-5 d)	Visit 4 8 Week Follow up (+/- 3-5 d)	Visit 5: 12 Week Follow Up (+/- 3-5 d)	Visit 6: 24 Week Follow Up (+/- 1 week)	Visit 7: 60 Week Follow Up (+/- 1 week)
Read and Sign Informed Consent	Х						
Medical History	Х						Х
Review of Immunosuppresants	Х	Х	Х	Х	Х	Х	Х
Interview, brief physical	Х	Х	Х	Х	Х	Х	Х
Vital Signs (heart rate, blood pressure, temperature)	Х	Х	Х	Х	Х	Х	Х
Missing HBV blood testing*	Х						
Quant anti-HBs	X [≠]	Х	Х	Х	Х	Х	Х
CRP**		Х	Х	Х	Х	Х	Х
Pregnancy test [¥]	Х	Х	Х		Х	X _∞	
Hepatic function panel		Х	Х	Х	Х	Х	Х
Patient Related Outcome Form for Inflammatory Disorder		Х	Х	Х	Х	Х	Х
Repository Blood Sample (for repeat antibody test)		Х	Х	Х	Х	Х	Х
Vaccine Administration, with observation for reactions		Х	Х		X***		
Adverse effects form [±]			Х	Х	Х	Х	Х

^{*} Test for anti-HBs, anti-HBc, or HBsAg if not in the medical record or > one year previously. Test for HIV and HCV antibody is not within 4 months of screening.

[≠] Only done at this visit if medical record indicates patient is anti-HBs positive by qualitative testing.

^{**} This will only be done in patients taking TNF or interleukin inhibitor therapy for chronic inflammatory disorders.

[¥] If potentially child bearing female. Patients who are positive will not be eligible.

^{***} A 3rd dose will be offered to those participants who lack seroprotection (>10 mIU/ml) at week 8.

[±] Observation for adverse events includes weekly telephone calls for 4 weeks after each vaccine dose.

 $[\]infty$ If patient requires third dose of vaccine as per protocol.

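### The 28-day adverse-event endpoint is a single per-subject proportion over a number of post-dose windows that varies with titre, so it cannot separate a third dose's added exposure from group susceptibility

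*Protocol*

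**What the plan says.** Safety is one of two co-primary objectives (Protocol 5.0 and 10.1). The first safety endpoint in 10.1 is "Proportion of subjects with unsolicited AEs after inoculation", and the events are "recorded for a period of 28 days after vaccine administration". No per-dose denominator is given. The Table 1 footnote makes the window recur: "Observation for adverse events includes weekly telephone calls for 4 weeks after each vaccine dose".

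Section 4.7 ties the number of doses to titre. If anti-HBs is at least 300 mIU/mL "after a single dose of vaccine, patients will not be given a second dose"; the protocol calls this unlikely. Subjects without a protective level at week 8 "will be given a third identical dose of vaccine at the week 12 visit". Dosing also ends early for safety reasons (6.7, 7.3), and a hold under 7.4 items 1 or 3 stops further doses for a whole group.

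On comparisons, 11.1 calls the study exploratory and descriptive, then adds: "Qualitative and quantitative differences between subgroups will be analyzed by Chi-square" or Fisher's exact test for categorical parameters, at p < 0.05.

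Other places describe a longer collection period:
- Section 5.0 requires "follow up of all patients for one year after the last dose of vaccine during which time all adverse events will be collected".
- Section 10.5 says Grade 1 and 2 events "will be collected at each visit and reported to the sponsor in a yearly report".
- Table 1 marks the adverse-effects form at every visit from week 4 to week 60.
- Item 1 itself goes on to have health changes recorded on the form at each visit.

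**The concern.** Each subject counts once, but the number of 28-day windows in which an event can be picked up differs between subjects, and it is linked to the other co-primary outcome. Poor responders get a third dose and with it a third window. Item 1 is not restricted to vaccine-related events, so the extra window also collects background illness.

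Two readings of the result are at stake. A group with weaker antibody response could look less well tolerated partly because it was vaccinated and called more often. And the effect of dose 3 itself is hidden in the pooled figure. Section 4.3 expects a third dose to cause little harm, on the basis of hemodialysis patients. The background section says this is the first known use of the vaccine with immunosuppressive therapy and in resolved hepatitis B. Dose-3 tolerability is therefore something this trial should display.

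**Working it through.** The protocol gives no adverse-event rate and no calculation for this endpoint, so there is no figure to reproduce.

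**Windows.** Doses fall at weeks 0, 4 and, if needed, 12. At 28 days each, active ascertainment is 28, 56 or 84 days (4, 8 or 12 weekly calls). Three doses against two is 84/56 = 1.5. As the one-dose path is called unlikely, 56 v 84 days is the practical contrast.

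**Expected proportion, 28-day-per-dose reading.** Assume every subject has the same chance p of at least one event in each window, independently across windows. Then P(any event) = 1 − (1 − p)^k for k windows. The values of p are assumptions.

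| p | 1 dose | 2 doses | 3 doses | 3 minus 2 | subjects of 6 |
|---|---|---|---|---|---|
| 0.05 | 0.050 | 0.098 | 0.143 | 0.045 | 0.27 |
| 0.10 | 0.100 | 0.190 | 0.271 | 0.081 | 0.49 |
| 0.20 | 0.200 | 0.360 | 0.488 | 0.128 | 0.77 |
| 0.30 | 0.300 | 0.510 | 0.657 | 0.147 | 0.88 |
| 0.50 | 0.500 | 0.750 | 0.875 | 0.125 | 0.75 |
| 0.70 | 0.700 | 0.910 | 0.973 | 0.063 | 0.38 |

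The difference is p(1 − p)², which peaks at p = 1/3 with 4/27 = 0.148. For a group of six that is 6 × 0.148 = 0.89, so the shift stays below one subject whatever p is. The last column supposes that all six in one group and none in the other receive dose 3. With 4 of 6 against 1 of 6 the gap is halved, to about 0.02 to 0.07.

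**Effect on the test.** In a 6 v 6 comparison at least one expected cell count is 3 or less, so Fisher's exact test is the natural choice of the two named. By exact enumeration (two-sided, 0.05), all-three-dose against all-two-dose groups reject with probability 0.0002, 0.0023, 0.0106, 0.0121 and 0.0022 at p = 0.05, 0.10, 0.20, 0.30 and 0.50. The value with equal two-dose exposure at p = 0.30 is 0.0063. Only the unrealistic contrast of all three-dose against all one-dose subjects passes 5%: 0.064 at p = 0.30 and 0.055 at p = 0.50.

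**Longer collection periods.** Treat p as the risk per four weeks throughout.
- One year after the last dose means 52, 56 or 64 weeks from day 0. At p = 0.05 the proportions are 0.487, 0.512 and 0.560; at p = 0.30 they are 0.990, 0.993 and 0.997. The three-to-two ratio at p = 0.05 falls from 1.46 on the 28-day reading to 0.560/0.512 = 1.09, although the absolute gap there (0.048) is about the same as before (0.045). At p = 0.30 the gap falls from 0.147 to 0.004.
- To week 60 for everyone, total time is equal and the effect of window length vanishes. Only the greater number of calls remains.

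**After the change.** Per dose, the expected proportion at equal risk is p in every window. Over the windows after doses 1 and 2 it is 0.51 at p = 0.30 for both two-dose and three-dose subjects, so the 0.147 artefact becomes 0.

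**The case against.** **The 28-day window is only one reading.** Sections 5.0 and 10.5, Table 1 and the rest of item 1 all point to collection beyond it, and the footnote says observation includes the calls, not that it consists of them. This stands: 28, 56 or 84 days cannot be stated as the settled observation period. It also shows that the period counting for item 1 is not fixed.

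**Tabulation is a matter for the statistical analysis plan.** This holds for table layouts, and nothing in 10.1 forbids per-dose tables. But the per-subject definition and the conflicting periods are in the protocol itself.

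**A third dose is real exposure.** This stands. The proportion validly describes the titre-guided regimen as given. It misleads only if read as per-dose tolerability or as a difference in susceptibility.

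**The size is small and rests on assumptions.** This stands too. Positive correlation between a subject's windows would generally narrow the gap, and complete correlation would remove it. No between-group test of adverse events is specifically named. The hold and termination rules use graded, related events, not this proportion.

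**Titre is not the only driver.** Correct. Group holds shorten exposure for unaffected subjects. A subject stopped because of an event has already met the binary endpoint.

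A reader might infer that poorly responding groups will falsely test as less safe, or that dose-3 risk is unrecoverable. The documents support neither. Rejection stays far below 5% in the two-against-three-dose contrast, and time since dose 3 can be derived from time since an earlier dose once dose dates are known.

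**Conclusion.** The point holds in limited form. On the 28-day-per-dose reading, item 1 is expected to run higher in subjects given a third dose, and in groups with more of them, at equal risk per window: 51% v 66% at an assumed 30%, 19% v 27% at 10%. This rests on equal and independent risk across windows, for which the protocol offers no data. It amounts to less than one subject in a group of six and does not inflate the error of the Fisher comparison.

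The harm is to the descriptive reading. Section 11.2 relies on the safety observations in 18 patients to judge whether further study is warranted, and a pooled per-subject figure cannot tell added exposure from group susceptibility or show what dose 3 contributes. The Appendix 1 form adds to this, since it relates events to doses 1 and 2 only. The change is worth making because it is cheap, not because the trial's conclusions are in danger.

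**What to change.** 1. Reconcile 10.1 item 1 with 5.0, 10.5 and Table 1, and state once which period counts for this endpoint.
2. For each dose, report subjects with at least one event within 28 days of that dose over subjects given that dose. Keep the per-subject figure beside it, with the number of doses shown.
3. In 11.1, make any between-group comparison of these events per dose, or over the windows after doses 1 and 2 among subjects who received both. Show one-dose and early-stopped subjects, and the dose-3 window, separately. Restricting to doses 1 and 2 without that condition would still mix unequal exposure.
4. Add a dose 3 column to the Appendix 1 form.

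The cost is wording in 10.1 and 11.1, one form column and a few more small tables. No visit, test or subject is added. Later-dose denominators will leave out subjects stopped earlier, which is why those subjects need their own line.

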10.5 Adverse Event Reporting

All grade 3 or 4 adverse events will be reported simultaneously to the IRB and sponsor within one week and 72 hours, respectively. Should a death occur, notification of the IRB will be within 24 -48 hours of receipt of this information. Events will be conveyed to the IRB and if needed to the sponsor in both electronic and hard copy form along with whether or not the event was considered to be related to administration of the study drug. All relevant lab studies will be included in the correspondence. All Grade 1 and 2 AEs (for example, such as those related to reactogenicity of the vaccine) will be collected at each visit and reported to the sponsor in a yearly report.

10.6 Definitions

An adverse event will be considered as "unexpected" if not included in the Investigator's Drug Brochure (Feb, 2019) or not listed at the specificity or severity observed in the study (Code of Federal Regulations Title 21, April 1, 2018). Definitions of grade severity of adverse events will be considered as follows:

Grade 1: mild, asymptomatic or mild symptoms; clinical or diagnostic observations only; intervention not needed.

Grade 2: Moderate; minimal local or noninvasive intervention indicated.

Grade 3: Severe or medically significant but not immediately life threatening;

hospitalization or prolongation of hospitalization indicated; disabling; limiting self care

Grade 4: Life threatening; urgent intervention needed

Grade 5: Death related to AE.

Adverse event: any untoward medical occurrence associated with the use of the vaccine

Serious adverse event: resulting in any of the following: death, potentially life-threatening, resulting in hospitalization, prolongation of hospitalization, persistent incapacity, substantial disruption of the ability to conduct normal life functions, or a congenital anomaly.

Medically attended adverse event (MAAE): any adverse event that leads to an evaluation by a healthcare professional.

Potentially immune mediated medical conditions (pIMMC): A list of these provided by the FDA is included in Appendix 4.

Grading of AEs will be according to Common Terminology Criteria for Adverse Events (CTCAE) Version 5.0, November 27, 2017 by the U.S. Department of Health and Human Services/National Institute of Health/National Cancer Institute.

10.7 Adverse Event Follow-up

Patients with grade 3 or greater AEs and all with SAEs including MAAEs will be seen no later than 48-72 hours of the time the event occurred. The patient will be followed by the principal investigator and/or referring specialist until resolution has been documented (regardless of relatedness consideration). Additional safety data will be included until at least week 52 after the last dose of vaccine.

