It is important to note that adverse event profiles did not differ between the vaccines used in these studies.⁵⁻⁸ One case of granulomatosis with polyangitis was reported 170 days after the second dose in the Heplisav B group but the collective data from these trials demonstrated that the vaccine did not induce autoimmune disorders at a higher than expected frequency (Dynavax Technologies, data on file) Moreover, the frequencies and titers of ANA and anti-dsDNA were comparable in the two vaccine treatment groups in these studies.

Potential Clinical Utility of a More Immunogenic HBV Vaccine

The development of a more immunogenic vaccine that induces rapid protection against HBV has particular relevance in situations where timely induction of neutralizing anti-HBs is desirable and

whenever attenuated responses to traditional HBV vaccine may otherwise be anticipated. Both of these issues are relevant in patients who are immunosuppressed due to medication. This is especially relevant in patients with resolved hepatitis B due to long term persistence of the genomic template for viral transcription in liver tissue and an inherent risk that hepatitis B viral reactivation may occur when immunosuppressed (see 1, below).

Thus, this protocol is an exploratory trial to assess the safety and effectiveness of Heplisav-B in three common clinical situations where patients are medically immunosuppressed: (1) in patients given tumor necrosis factor (TNF) or interleukin inhibitor therapy for chronic inflammatory disorders; (2) in patients placed on cancer chemotherapy for solid organ malignancy; and (3) in patients who are immunosuppressed after liver transplantation either done for a) chronic hepatitis B or for b) the same or other indications during which they receive a liver from an anti-HBc positive donor.

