9.2 Method and Timing

Assessment of efficacy will require quantitative anti-HBs assessments at each of the visits that are specified in Table 1. This includes week 4,8,12, 24 and 60 week visits.

10. 0. ASSESSMENT OF SAFETY

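### No safety contact is scheduled between weeks 24 and 60, so for most of the year after the last dose event capture and the 48-72 hour rule depend on patients reporting unprompted

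*Protocol*

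**What the plan says.** **What is to be captured.** Section 5.0 makes safety one of two co-primary objectives, with follow-up for a year after the last dose. Section 10.1, item 2, states: "The study will capture all SAEs (and Grade 3 AEs) that occur through one year after the last dose of vaccine". Items 3 and 4 set the same period for MAAEs and pIMMCs. Item 5 covers increases in immunosuppression, using medication records over 12 months.

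**How fast.** Section 10.1, item 2, says "all patients with these events will be seen within 48 to 72 hours and acted upon if needed", and items 3 and 4 refer back to it. Section 10.7 applies the limit to Grade 3 or worse AEs and to SAEs including MAAEs, who "will be seen no later than 48-72 hours of the time the event occurred". Section 10.6 defines an MAAE broadly: an AE that leads to any evaluation by a healthcare professional.

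**How the site learns of events.** The Table 1 footnote reads: "Observation for adverse events includes weekly telephone calls for 4 weeks after each vaccine dose". Section 10.1, item 1, says that adverse events "will be recorded for a period of 28 days after vaccine administration, and at each visit changes in the patient's state of health will be" entered on the AE form. The post-baseline visits in Table 1 match Section 9.2: "This includes week 4,8,12, 24 and 60 week visits". Section 10.4 also asks patients to report as needed after each dose. The Appendix 2 forms have a box for a visit between the specified ones.

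**The concern.** The Protocol promises a full year of capture for the most important event classes, but its scheduled contacts are concentrated in the first weeks. After the week 24 visit the site next asks the patient anything at week 60.

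The Protocol's own background shows that late immune-mediated events are possible: "One case of granulomatosis with polyangitis was reported 170 days after the second dose". With dose 2 at week 4, that timing falls in study week 28, shortly after the scheduled contacts thin out.

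Two things are at stake:

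- **The endpoints.** These are proportions of subjects with an event, in groups of 6. One affected patient who goes unrecorded changes a group proportion by 1/6, or 17 percentage points.
- **The safety rules.** The holds in Section 7.4 and the terminations in Section 11.4 can act only on events the site knows about.

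No analysis plan can repair this, because events that were not collected cannot be recovered in analysis.

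**Working it through.** The Protocol gives no figure of its own to reproduce here. The check is timeline arithmetic.

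**Inputs**
- Visits at weeks 0, 4, 8, 12, 24 and 60 (Table 1).
- Windows, Section 4.7: "The 12, 24, and week 60 visits will have a one week" margin either way.
- Doses at weeks 0 and 4, with a third at week 12 for non-responders (Section 4.7).
- Weekly calls for 4 weeks after each dose (Table 1).
- Capture period of 52 weeks after the last dose (Section 10.1).

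**Step 1: gaps between visits.** These are 4, 4, 4, 12 and 36 weeks. With windows, the last gap runs from (60 - 1) - (24 + 1) = 34 weeks to (60 + 1) - (24 - 1) = 38 weeks.

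**Step 2: share of follow-up with weekly calls.** Two doses: 8/60 = 13%. Three doses: 12/60 = 20%. Within the 52 weeks after the last dose, calls cover 4/52 = 8% in either case. These figures count calls only; the visits at weeks 8, 12, 24 and 60 also collect adverse events.

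**Step 3: share of the capture year that falls between the week 24 and week 60 visits.**

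| Doses | Capture year (weeks) | Part in the gap | Share |
|---|---|---|---|
| 0, 4 | 4 to 56 | 24 to 56 = 32 weeks | 32/52 = 62% |
| 0, 4, 12 | 12 to 64 | 24 to 60 = 36 weeks | 36/52 = 69% |

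For three-dose patients the capture year also runs 4 weeks past the last visit. That is a separate matter.

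**Step 4: the 48-72 hour limit.** Suppose scheduled contacts were the only source of information. The gap is 36 × 7 = 252 days, and only an event in its last 3 days would be followed by a contact within 72 hours: 3/252 = 1.2%. This is a lower bound, since patients may call in.

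**Step 5: the cited late case.** Week 4 + 170/7 = week 28.3, inside the gap.

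**Step 6: can a late event bear on other patients' dosing?** The Protocol gives no accrual period, so this is conditional. The gap opens 24 weeks after the first patient's first dose. A later patient is still due a vaccination then if first dosed more than 24 - 4 = 20 weeks after the first patient (two doses), or more than 24 - 12 = 12 weeks after (third dose needed). With faster enrolment the dosing consequence disappears; the endpoint consequence remains.

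**Step 7: the starting points of the time limits.** Section 10.7 counts from when the event occurred. Section 10.1 names no starting point. For deaths, Section 10.5 counts notification of the IRB from receipt of the information. The last is a reporting limit rather than a limit for seeing a patient, but the Protocol is using different starting points without saying why.

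**The case against.** A reader might infer that there is no contact at all after week 24, that the 48-72 hour rule cannot be met, and that the one-year endpoints rest on recall alone. The Protocol does not support any of these. Section 10.4 asks for as-needed reporting, Section 10.1 foresees patient photographs between visits, and the Appendix 2 forms provide for in-between visits. The rule can be met whenever a patient reports promptly. Many SAEs and all MAAEs, by definition, involve medical care and so tend to leave records. Nor is ascertainment nil after week 8: Table 1 has an AE form, examination, immunosuppressant review and hepatic panel at weeks 12, 24 and 60, and medical history is retaken at week 60.

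Three further readings go too far:

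- **Clustering.** The endpoints count subjects with an event within a window. Misdating within the window leaves them unchanged; only omission matters, and its size is unknown.
- **The 170-day case.** It shows that late events occur, not that one would be missed. A serious diagnosed disease is unlikely to be forgotten at week 60, and the same sentence says autoimmune disorders were not more frequent than expected.
- **Patients receive no reporting instruction.** This cannot be concluded: the consent form is a separate document and is not available here.

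It can also be said that call frequency is a matter of judgement in an 18-patient descriptive study, and that weekly calls match the 28-day AE recording period. That is fair for routine AEs. It does not answer the point for the event classes that the Protocol says it will capture for a year. The body of the Protocol gives no route, time limit or duration for as-needed reporting, and the Appendix 2 forms cover inflammatory disorders (Group A) only. The weekly safety review in Section 15.0 can consider only what has reached the site.

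**Conclusion.** The point holds as a mismatch between what is promised and what is scheduled. No safety contact is scheduled for 36 weeks (34 to 38 with windows), which is 62% of the year after dose 2 and 69% of the year after a third dose. In that interval, capture and the 48-72 hour rule depend on unprompted patient reports, and otherwise on recall and records at week 60. Late events may be missed, or may reach the hold and termination rules late.

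The result assumes nominal dosing at weeks 0, 4 and, where needed, 12. The effect on holds and terminations also assumes that enrolment or dosing is still under way when the late event occurs, and that the patient does not report it. The number of events that would be lost cannot be estimated from the Protocol.

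This should be changed because it touches a co-primary objective and is cheap to mend; it does not invalidate the design.

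**What to change.** 1. **Add interim safety calls to Table 1 and Section 10.4.** The existing coordinator would make a brief scripted call, for example every 4 to 6 weeks between the week 24 and week 60 visits. It would ask about SAEs, MAAEs, new pIMMCs and changes in immunosuppressants, with answers recorded on the Appendix 1 form.
2. **Reconcile the time limits.** Sections 10.1 and 10.7 should be made consistent with each other and with the contact schedule, and the difference in starting point from Section 10.5 should be resolved or explained. Which limit is right is for the sponsor and the investigator to decide.

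**Cost.** Every 6 weeks gives calls at weeks 30, 36, 42, 48 and 54, which is 5 per patient and 5 × 18 = 90 in all. Every 4 weeks gives weeks 28 to 56, which is 8 per patient and 8 × 18 = 144 in all. No visit or procedure is added. The downside is modest coordinator time and possibly a higher count of late events, which would reflect fuller capture.
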